[name] [name] [name] [name]	FISABIO GSK GSK GSK	Medical Doctor Epidemiologist Medical expert Statistician	Supervision and medical consultant Supervision and advice Supervision and advice Supervision and advice

1. Rationale and background

COVID-19 is an infectious disease caused by the severe acute respiratory syndrome coronavirus 2 (SARS-CoV-2) first identified in Wuhan, China, in December 2019 (1). As of March 10th, 2021, COVID-19 pandemic has resulted in more than 117 million confirmed cases and above 2.6 million deaths worldwide (2). Therefore, SARS-CoV-2 outbreak has led to the largest and more severe pandemic since the influenza pandemic in 1918-19 (3). Spain ranks as the seventh most affected country with more than 3 million cases and 71,727 deaths (2). To date, the Spanish region Community of Valencia has registered 381,919 positive cases and 6,911 deaths (4).

SARS-CoV-2 infection may be asymptomatic or cause a wide spectrum of symptoms that may appear after a variable period of incubation (average time from exposure to onset is 5 days; 97.5% of people who develop symptoms do so within 11.5 days) (5). Among them, the most common symptoms derive from the primary infection of the respiratory tract and consist of dry cough, shortness of breath and fever (5). Additional symptoms include fatigue and changes to taste and smell (5, 6). However, SARS-CoV-2 infection has also been associated with alterations in the CNS and peripheral nervous system (7), liver (8), cardiovascular system (9), kidneys (10) and skin (11, 12).

Cutaneous manifestations of COVID-19 were first reported in early 2020 in China with only 2 out of 1,099 positive cases (13). However, a study carried out later in Italy found that 18 out of 88 COVID-19 positive patients developed dermatological alterations, of which 8 developed cutaneous involvement at the onset and 10 after the hospitalization. Cutaneous manifestations included erythematous rash (14 patients), widespread urticarial (3 patients) and chickenpox-like vesicles (1 patient) (14). Since then, several studies have discussed reports of patients infected with COVID-19 associated with vesicular manifestations of Herpes Zoster (HZ) (15, 16, 17, 18). A recent Turkish publication collecting data from fifteen tertiary hospitals from 13 provinces described an increase in the number of HZ diagnoses when comparing two months periods pre and post onset of the pandemic (19). These results are consistent with a latter study carried out in Brazil in which the number of HZ cases were quantified during the months of March to August from 2017 to 2019 and compared with the similar period in 2020 (20). Although the HZ cases were not assessed within COVID-19 positive patients, an extra 10.7 cases per million inhabitants during the pandemic was reported, which might suggest a correlation between both diseases.

HZ is a severe disease resulting from the reactivation of Varicella Zoster Virus (VZV), which remains latent in sensory nerve ganglia after primary infection (Varicella) (21). HZ can result in dermatomal chronic pain which is its most common complication (post-herpetic neuralgia, PHN) (22). Many patients with PHN go on to develop severe physical, occupational, and societal disabilities because of the enduring pain. Both, HZ and PHN result in reduced quality of life as well as individual and societal health care costs (23).

VZV reactivation seems to be a result of a waning of VZV-specific cell-mediated immunity as occurs with ageing or in subjects with immunosuppressive disorders (24). SARS-CoV-2 infection is associated with lymphopenia with reduced numbers of CD4 + and CD8 + T cells, B cells and natural killer (NK) cells (25). Because cell-mediated immunity is key in the protection against HZ (26), lymphopenia could predispose COVID-19 patients to HZ development. However, more scientific evidence needs to be provided to corroborate this hypothesis.

Based on the potential association between SARS-CoV-2 and HZ, we propose here a study to estimate the risk of HZ in subjects with SARS-CoV-2 infection using Real World Data (RWD). This population-based retrospective dynamic cohort study (meaning that members can leave or be added over time) will be based on eHR databases/registries from the Valencia Region (Valencia

Health System Integrated Database (VID) (27). VID allows linking socio-demographic, inpatients, outpatients, specialists, medication, and microbiology databases (among others) at individual level. The study population will consist of all population covered by the Public Health System (over 98%), representing about 5 million persons. As of March 8th, 2021, more than 381,919 confirmed cases of SARS-CoV-2 have been registered in the Valencian Community (4). Together with the VID makes the region of Valencia the ideal candidate to test the proposed hypothesis.

2. Hypothesis

We hypothesize that individuals 50 years and older previously infected with SARS-Cov-2 have higher risk of experiencing Herpes Zoster.

3. Objectives

The overall objective is to estimate the risk of HZ in subjects 18 years and older infected with SARS-CoV-2 using the Valencia health system Integrated Databases (VID).

3.1 Primary objectives

Compare the risk of HZ among individuals 50 years and older with and without laboratory confirmed SARS-CoV2 infection.

3.2 Secondary objectives

Compare the risk of HZ among individuals 18 years and older with and without laboratory confirmed SARS-CoV2 infection.

Compare the risk of HZ in overall population older than 18 years old in the pandemic period against pre-pandemic period.

Describe the likelihood of developing HZ after laboratory-confirmation of SARS-CoV2 according to severity of disease.

3.3 Exploratory objectives

Describe the changes with time in likelihood of developing HZ after laboratory-confirmation of SARS-CoV2.

4. Methods

4.1 Study design

A population based, retrospective dynamic cohort study using real-world data from the Valencia healthcare Integrated Databases (VID).

Individuals within the cohort will be followed up over time to determine the incidence of HZ. As a dynamic cohort, individuals will be recruited to or leave the cohort at different times depending on the inclusion/exclusion criteria.

4.2 Study population and period

The cohort will include all subjects older than 18 years living in Valencia Region, registered in the Regional Health System (RHS) (over 98%) from January 1st 2018 to, at least, December 31st 2020 (or date of data extraction). The inclusion and exclusion criteria will be the following:

Inclusion criteria: Subjects aged 18 years and above covered by the RHS and residing in the Valencia Region during study period.

Exclusion criteria:

- Subjects with less than 12 months of registration to the RHS and subjects with incorrect codification.
- Subjects vaccinated against HZ before the diagnosis of SARS-CoV-2
- Subjects vaccinated against SARS-CoV-2 before the diagnosis of SARS-CoV-2

Start of follow-up: The start of the follow-up is defined as the latest of start of the study (1st January 2018), first date of registration in the database or date of the 18th birthday.

End of follow-up: The end of the follow-up is defined as the earliest of the following cases:

- End of study period
- Loss of follow-up (exit of RHS)
- Exitus
- Vaccination with HZ vaccine
- Vaccination with COVID-19 vaccine
- Development of HZ

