4.5 Other health outcomes

4.5.1 Pandemic and pre-pandemic periods

- Pre-pandemic period will be considered from January 1st 2018 to March 14th 2020
- Pandemic period will be considered from March 14th 2020 to the end of study period

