4.6 Covariates

Covariate information will be collected on sociodemographic, spatial information, vaccination against Sars-Cov-2 and comorbidities. The source of the eHR databases and the variables needed to create the covariates is given in Annex 1.

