4.9.9 Secondary objectives

- 1) A statistical analysis like the previous one will be developed to compare the risk of HZ among individuals 18 years and older between SARS-CoV2-free and lab-confirmed.
- 2) The risk of HZ in subjects with Sars-Cov-2 exposed (pandemic) respect to subjects unexposed (pre-pandemic) will be estimated by a multivariate Poisson or negative binomial model according to applicability assumptions. Age, sex and comorbidities will be considered for the adjustment.

3) Describe the likelihood of developing HZ after laboratory-confirmation of SARS-CoV2 according to severity of disease.

We will calculate and compare the predicted probability of developing incident HZ in the 1, 3, 6 months following Sars-Cov-2 (1, 3, 6 – months cumulative incidence) using logistic

regression models. We will compare the overall probability, regarding Sars-Cov-2 severity, and the probabilities obtained from models adjusting for the abovementioned covariates (See section 3.5).

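### Secondary objective 2 names the overall adult population, but follow-up ends at COVID-19 vaccination and the study end is open, so its rate ratio may not describe that population

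*Protocol*

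**What the plan says.** - **Target.** Protocol section 3.2 states the objective as "Compare the risk of HZ in overall population older than 18 years old in the pandemic period against pre-pandemic period".
- **Periods.** Section 4.5.1: "Pre-pandemic period will be considered from January 1st 2018 to March 14th 2020", and "Pandemic period will be considered from March 14th 2020 to the end of study period". Section 4.2 sets the study period as "from January 1st 2018 to, at least, December 31st 2020 (or date of data extraction", so the end is a minimum and not a fixed date.
- **Follow-up.** Section 4.2 has one end-of-follow-up list for the whole cohort. One of its events is "Vaccination with COVID-19 vaccine". No objective is exempted. Section 4.4 defines pandemic time as follow-up from the start of the pandemic, so this list cuts it.
- **Exclusion.** The same section also excludes "Subjects vaccinated against SARS-CoV-2 before the diagnosis of SARS-CoV-2".
- **Model.** Section 4.9.9, item 2, estimates "The risk of HZ in subjects with Sars-Cov-2 exposed (pandemic) respect to subjects unexposed (pre-pandemic" by Poisson or negative binomial regression, with age, sex and comorbidities considered for adjustment. It gives no follow-up rule of its own.
- **Covariates.** Section 4.6: "Covariate information will be collected on sociodemographic, spatial information, vaccination against Sars-Cov-2 and comorbidities".

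**The concern.** The objective asks about everyone, while the follow-up rule keeps only time before COVID-19 vaccination. Because the pre-pandemic period closes on 14 March 2020, the rule acts on one side of the comparison only. Once vaccination starts, the retained pandemic time belongs increasingly to people who are vaccinated late or never. If they differ in health or in use of the public system in ways that age, sex and the listed comorbidities do not capture, the rate ratio mixes that selection with the pandemic effect. Listing vaccination as a covariate does not help: in time that ends at vaccination, the variable never changes.

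With millions of person-years the interval will be narrow, so even a small distortion could look like a finding.

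**Working it through.** **1. The plan's own figures.** The protocol gives no precision or power figure for secondary objective 2. Its one power figure (0.760864, section 4.9.5) belongs to the comparison of laboratory-confirmed with SARS-CoV-2-free subjects. It reproduces at 0.759 (pooled-variance rate difference, one person-year per subject, two-sided 0.05) and has no bearing here.

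**2. Period lengths from the stated dates.** Pre-pandemic, 1 January 2018 to 14 March 2020: 2.198 years. Pandemic to 31 December 2020: 292 / 365.25 = 0.799 years.

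**3. Person-time lost to vaccination censoring.** The documents give no uptake. Assumed: none before 31 December 2020, then a linear rise to final coverage u on 31 October 2021, flat afterwards. The later end dates are also assumptions. Share lost = (area under the uptake curve) / (pandemic years).

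| Study end | Pandemic years | Share after 2020 | Lost, u = 20% | u = 50% | u = 80% |
|---|---|---|---|---|---|
| 31 Dec 2020 | 0.80 | 0% | 0% | 0% | 0% |
| 31 Jul 2021 | 1.38 | 42% | 2.9% | 7.3% | 11.7% |
| 31 Oct 2021 | 1.63 | 51% | 5.1% | 12.8% | 20.4% |
| 31 Jan 2022 | 1.88 | 58% | 7.1% | 17.7% | 28.4% |

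The same rule removes 0% of pre-pandemic time in every row.

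**4. Possible distortion with a true period ratio of 1.** Let q be the share of pandemic time discarded, and r the HZ rate in discarded time relative to retained time, within strata of the model's covariates. The estimated ratio is 1 / [(1 − q) + q·r].

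| q | r = 0.8 | r = 1.25 | r = 1.5 |
|---|---|---|---|
| 0.10 | 1.020 | 0.976 | 0.952 |
| 0.20 | 1.042 | 0.952 | 0.909 |
| 0.30 | 1.064 | 0.930 | 0.870 |

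**5. Cross-check from the never-vaccinated share.** Assume an end on 31 January 2022, coverage v = 0.8 and uniform uptake over January to September 2021 (mean 0.375 years unvaccinated in 2021 among those vaccinated).
- Retained time per person = 0.8 × (0.799 + 0.375) + 0.2 × (0.799 + 1.084) = 1.316 of 1.883 years, so 30% is lost.
- Never-vaccinated share of retained time: s = 0.2 × 1.883 / 1.316 = 0.286, against 0.20 before the pandemic if no one is excluded.
- With k the never-vaccinated HZ rate relative to the vaccinated, the ratio is [1 − s(1 − k)] / [1 − (1 − v)(1 − k)].
- k = 0.5 gives 0.857 / 0.900 = 0.952. k = 1.25 gives 1.0715 / 1.05 = 1.02. The sign depends on k.

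**6. Precision.** With 4,000,000 adults (section 4.9.1) and 5.02 per 1000 person-years (section 4.9.2), 20,080 events are expected per year.
- Pre-pandemic: 2.198 years, 44,146 events.
- Pandemic to 31 December 2020: 0.799 years, 16,053 events. Half-width = exp(1.96 × √(1/44,146 + 1/16,053)) − 1 = 1.8%.
- Pandemic with 1.316 retained years: 1.316 × 20,080 = 26,425 events. Half-width = exp(1.96 × √(1/44,146 + 1/26,425)) − 1 = 1.5%.

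These are pure Poisson figures; overdispersion would widen both.

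**The case against.** **The harm is conditional.** The only date the protocol states for the end of the study is 31 December 2020, as a minimum, and with that end the loss is essentially nil if vaccination had hardly begun. This stands, but the protocol does not fix that end. The extraction row of the Timelines chart appears to carry marks in July 2021, October 2021 and January 2022. The chart's text is damaged and its marks have no clear legend, and an extraction date need not be a data cut-off, so nothing here rests on it.

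**The comparator may not be unrestricted.** A reader might infer that the pandemic arm shrinks to unvaccinated people while the pre-pandemic arm keeps everyone. The censoring rule alone would do that. The exclusion in section 4.2, applied to whole subjects, would also remove pre-pandemic time, selected on a later event. The imbalance in step 5 (0.286 against 0.20) would then not arise as computed. The bullet is also unclear for vaccinated people who are never diagnosed. The documents therefore do not support the claim of an unrestricted comparator. They do support the narrower point that neither reading yields the overall population.

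**Some handling exists.** Sections 4.6.4 and 4.9.8 provide for calendar week, month and year, so descriptive rates can be separated in time. Adjustment in section 4.9.9 removes selection that age, sex and comorbidities explain. Neither corrects the model's period rate ratio for what remains.

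**Conclusion.** The mismatch between objective and follow-up rule is in the text and holds, conditionally on a study end in the vaccination era. It affects one secondary objective and the descriptive period rates.

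Its size is unknown. The illustrative range of about 0.87 to 1.06 rests on 10–30% of pandemic time being discarded and on a residual rate in discarded time of 0.8 to 1.5 times that in retained time. Neither input comes from the documents. Much of that range lies outside a 1.5% half-width, and its extremes are comparable to the 10% effect used in the protocol's power calculation.

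A reader might also infer that the ratio must be biased downward, because never-vaccinated people seek care less. Nothing in the documents fixes that direction, and step 5 shows it reversing with the assumed relative rate.

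**What to change.** - **Section 4.5.1.** For secondary objective 2 and the descriptive period rates, give the pandemic period a fixed end: 31 December 2020, or the day before COVID-19 vaccination began in the region.
- **Section 4.2.** State that, for this objective, the vaccination exclusion is not applied on events after that date and vaccination is handled only by censoring. Without this, a fixed end date would not be enough: data extracted later could still drop people vaccinated in 2021 from both periods.
- **Later time.** If kept, report it as a separate analysis labelled as person-time not vaccinated against COVID-19.
- **Section 4.6.** Keep collecting COVID-19 vaccination dates, since the rules in 4.2 need them. The vaccine variables in Annex 1 name only pneumococcal vaccines, so 4.6 is the only explicit statement that these data are collected. State that vaccination is not a model covariate, because it is constant in retained time.

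The change is wording only and needs no new data. The cost is less pandemic person-time for this objective, and hence the small loss of precision shown in step 6.

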4.3 Case definition of HZ

Incident herpes zoster cases will be considered as the appearance of a HZ-related ICD-code (ICD-9 053.x; ICD-10 B02.x) diagnostic code for herpes zoster, excluding those with specific ICD-codes for PHN (ICD-9 053.12, 053.13 and 053.19, ICD-10 B02.2). Cases will be identified from outpatient, SIA (see section 4.8), and inpatient, MBDS, in any diagnostic position. Incident HZ will be defined as an episode of herpes zoster without any evidence of herpes zoster or PHN for at least 6 months previously.

4.4 Sars-Cov-2 exposure

Exposure status of everyone might change within the follow up period (Figure 3): Sars-Cov-2 unexposed in the pre-pandemic period and Sars-Cov-2 exposed in the pandemic period. Sars-Cov-2 exposure levels will be treated as a time-varying variable and the following states will be considered:

- 1) **Sars-Cov-2 unexposed**: subject's follow up period from the start of follow-up to the declaration of the pandemic in Spain (March 14th 2020).
- 2) **Sars-Cov-2 exposed**: subject's follow up period from the start of the pandemic. We will consider the following 2 comparison groups:
 - **Sars-Cov-2 free**: time from the start of pandemic (or the follow-up) to the date of the first Sars-Cov-2 confirmation (by PCR or Ag test). If no Sars-Cov-2 positive test registered, the time period will be until the end of follow-up.
 - **Sars-Cov-2 laboratory-confirmed**: time from the date of the SARS-CoV-2 positive result in RedMiva to the end of follow up.

[figure not shown]

Figure 3. Example of exposure, follow-up and comparisons in the study.

* Subjects with recurrent episodes of Sars-Cov-2 will be treated separately. If the sample size is not large enough for the analysis, these individuals will be excluded for the analysis.

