4.9.6 Primary objective

To develop the primary objective, we will compare the incidence of HZ among SARS-Cov-2 free and Sars-Cov-2 laboratory-confirmed subjects 50 years and older during the pandemic period. For this purpose, models using individual patient data or grouped will be implemented.

[figure not shown]

Figure 4: Cohort diagram for HZ rates comparison among subjects with and without previous episode of COVID19

The risk of HZ in subjects with Sars-cov-2 respect to subjects without Sars-Cov-2 will be estimated by a multivariate Poisson or negative binomial model according to applicability assumptions. Individual data will be grouped by SARS-Cov-2 free and Sars-Cov-2 laboratory-confirmed exposure, age, sex and comorbidities. Individual and grouped data can both be analyzed with the Poisson (or Negative binomial) distribution. Given the usual large size of the cohort, estimation when using grouped data is considerably quicker than when using individual level data and the results for both approaches are remarkably similar.

The number of HZ cases by aggregation unit will be compared among SARS-Cov-2 free and labconfirmed subjects. Age, sex, and comorbidities will be considered for the adjustment, and the person-time-at-risk (in years) as an offset term. RR and their 95% confidence or credible intervals will be reported.

Besides, individual-level risk of HZ between SARS-Cov-2 free vs lab-confirmed will be estimated by Cox regression model for right censored data. The abovementioned variables will be also considered for the adjustment.

Both approaches will be performed and compared for the robustness of the results.

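### The primary RR pools all time after a positive test up to an open study end, so if the excess risk of HZ fades, its size depends on the data cut-off

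*Protocol*

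**What the plan says.** - **Exposure.** Section 4.4 defines the laboratory-confirmed state as "time from the date of the SARS-CoV-2 positive result in RedMiva to the end of follow up". It is a single state without subdivision.
- **Primary models.** Section 4.9.6 groups the data by exposure, age, sex and comorbidities and fits a Poisson or negative binomial model with "the person-time-at-risk (in years) as an offset term". The individual-level risk is also "estimated by Cox regression model for right censored data". Neither description mentions time since the positive test.
- **Study end.** The cohort in section 4.2 runs "from January 1st 2018 to, at least, December 31st 2020 (or date of data extraction"). Section 4.5.1 inherits that end: "Pandemic period will be considered from March 14th 2020 to the end of study period". Section 4.8 also treats 31 December 2020 as a minimum, and the extraction period in Annex 1, item 3.1, stops in January 2015, so it cannot settle the matter.
- **Mechanism.** The rationale says that "lymphopenia could predispose COVID-19 patients to HZ development". It gives no duration and asks for more evidence.
- **Timing elsewhere.** Secondary objective 3 (section 4.9.9) compares "the predicted probability of developing incident HZ in the 1, 3, 6 months following Sars-Cov-2" by severity. The exploratory objective (sections 3.3 and 4.9.10) describes time from infection to HZ.

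**The concern.** A single RR over all confirmed time is a person-time-weighted average of the RRs at each interval since infection. If those RRs differ, the weights matter, and the weights are set by how long follow-up runs after the 2020 infections. With the end date open, an administrative date helps to decide what the primary estimate averages over.

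Two consequences follow if the excess is short-lived. A later extraction adds events but pulls the RR towards 1, so a null primary result could not be read as no excess after infection. Estimates from different cut-offs would also not be comparable.

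The timing analyses already planned do not fill the gap. The 1, 3 and 6-month probabilities are compared by severity after confirmation, and the exploratory analysis summarises time to HZ among cases after infection. Neither gives a confirmed-versus-free RR for a defined period.

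**Working it through.** **The plan's own figure.** The protocol gives no figure for this point. Its power figure in section 4.9.5 does reproduce: rates of 7.0 and 7.7 per 1000 and 2,000,000 and 110,000 units give a two-sided power of 0.759 (pooled score test) to 0.768 (Wald test on the log RR), against 0.760864 stated. This holds only if each person counts as one full person-year. It is no evidence for the concern, but it sets RR 1.1 as the effect the study aims to detect.

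**Inputs.** Positive results from March to December 2020 (section 4.9.4): 13,009; 11,215; 2,709; 976; 4,900; 26,679; 28,181; 49,209; 70,279; 81,108. They are spread evenly within each month, with March starting on the 14th. Assumptions that are not in the protocol: RR 1.5 for W days after the positive test, then RR 1; W = 30, 90 or 180 days, after the protocol's 1, 3 and 6 months.

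**Formulas.** With n(d) positives on day d and end date T:

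- share of confirmed time within W days: f = Σ n(d)·min(T−d, W) / Σ n(d)·(T−d)
- pooled RR = 1 + (1.5 − 1)·f

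For example, at 31 December 2020 with W = 90, f = 0.696 and the RR is 1 + 0.5 × 0.696 = 1.35.

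**Results for 2020 infections, no other censoring**

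| End date | Mean confirmed days | Share within 30 / 90 / 180 days | Pooled RR if excess lasts 30 / 90 / 180 days |
|---|---|---|---|
| 31 Dec 2020 | 80 | 32% / 70% / 90% | 1.16 / 1.35 / 1.45 |
| 30 Jun 2021 | 261 | 12% / 34% / 69% | 1.06 / 1.17 / 1.34 |
| 31 Dec 2021 | 445 | 7% / 20% / 40% | 1.03 / 1.10 / 1.20 |

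**With vaccination censoring.** Section 4.2 ends follow-up at COVID-19 vaccination. Suppose the 381,919 − 288,311 = 93,608 further cases to 8 March 2021 are added, evenly from 1 January, and 90% of subjects are censored evenly over March to June 2021 (assumed). The 90-day share is then 48% at 30 June and 43% at 31 December 2021, so the pooled RR is 1.24 and 1.22. For a 30-day excess it is 1.08 at both dates.

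**Could a null hide a short excess?** Take 110,000 confirmed subjects, 7 per 1000 person-years, and 31 December 2020 as the end. Confirmed time is 110,000 × 79.9 / 365.25 ≈ 24,060 person-years, or about 168 events at RR 1. If the RR is 1.5 for 30 days, the pooled RR is 1.16 and power is about 0.55. In the 30-day window alone it is about 0.95. With the end at 31 December 2021 and no other censoring, the two figures are about 0.17 and 0.98.

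**The case against.** The strongest reply is that the protocol never says the excess is short-lived. The rationale gives lymphopenia no duration, the hypothesis concerns people previously infected, and the primary objective compares people with and without confirmed infection. An average RR over ever-infected time answers that question and is a legitimate estimand. With a constant RR there is no dilution. All of this stands. A reader might infer that the primary RR is wrong or contradicts the stated mechanism; the documents do not support that.

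It also stands that exposure does not run indefinitely. HZ, HZ vaccination, COVID-19 vaccination, death and exit all end it, so the uncensored 2021 rows above mark the severe end. Under the assumed vaccination scenario, drift between June and December 2021 almost disappears. The fall from 1.35 at the minimum end date remains.

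A reader might also infer from the timeline chart that data will run to January 2022. The chart's marks in the extraction row may denote follow-up meetings, and an extraction month is not a data cut-off. The chart shows only that no cut-off is fixed.

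Finally, windows and cut-off dates are often left to a SAP, which is not shown here. But the protocol itself fixes the exposure as one undivided state and words its end as a minimum, so the point can fairly be raised on the protocol.

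**Conclusion.** The concern holds in a conditional form. The primary RR pools all confirmed time, and its end date is open. If the RR varies with time since infection, the estimate depends on the cut-off, and a null result would not exclude a short-lived excess.

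The size depends on the assumed duration. At 31 December 2020 an RR of 1.5 appears as 1.45 if it lasts 180 days, 1.35 if 90 and 1.16 if 30. By 31 December 2021 the 90-day case lies between 1.10 (no other censoring) and about 1.22 (assumed vaccination censoring).

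These figures rest on all-age positive results, while the primary population is 50 and older. The table counts 288,311 positive results in 2020, against 219,144 confirmed cases as of January 2021 in section 4.9.3, so the shares are approximate. They apply to the Poisson model; a single Cox hazard ratio would also average over time, with different weights.

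A further inference, that the primary RR should be confined to 0-180 days, is not supported. The protocol lists 1, 3 and 6 months without preferring one, and the change barely helps. At 31 December 2020 it gives 1.18 instead of 1.16 for a 30-day excess and 1.39 instead of 1.35 for a 90-day excess. Without other censoring it still falls, to 1.08 and 1.25, at both 2021 dates.

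**What to change.** 1. Keep the overall laboratory-confirmed versus SARS-CoV-2-free RR as the primary estimate.
2. In sections 4.4 and 4.9.6, prespecify in the same Poisson and Cox models RRs for confirmed time split at 0-30, 31-90, 91-180 and over 180 days since the positive test, each against SARS-CoV-2-free time. These cut points are the protocol's own horizons.
3. In sections 4.2, 4.5.1 and 4.8, name one data cut-off date for all registries before extraction, and bring the Annex 1 period into line.

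The cost is low. RedMIVA already supplies test and result dates, and section 4.9.8 already splits follow-up by time-varying covariates, so this adds one more split. The price is precision: at 31 December 2020 the roughly 168 events expected at RR 1 would divide into about 54, 63, 34 and 17 across the four windows (shares 32.2%, 37.4%, 20.0% and 10.4%), so each interval will be wider than the overall one.
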